¹¹ The clinical course of each AE should be followed until resolution, stabilization, or until it has been determined that the study treatment is not the cause.

Title: Direct Peritoneal Resuscitation in Gastroschisis

PI: [name]

Sponsor: UAMS

Schedule of Procedures and Assessments

Screening (Day of Birth from 0-12 hours)

- Informed Consent
- Randomization
- Silo placement (within 2 hours of admission to the NICU)
 - JP drain placed and secured per randomization
- Vital signs: heart rate (HR), respiratory rate (RR), MAP/BP, pulse oximetry (SpO₂)
- Weight
- Routine Daily labs per NICU standard practice:
 - Complete CBC
 - Magnesium
 - Renal Function Panel (sodium, potassium, chloride, CO₂, BUN, creatinine, calcium, phosphate, albumin, glucose)
- Research lab (both groups):
 - Lactate
- G-tube placement per NICU standard practice

Staged Reduction Day 1 (Day of Birth from 0-24 hours)

- Verify laboratory values for eligibility
- Instill DPR for DPR group every 6 hrs (± 30 minutes)
- Blood glucose within 1 hour prior to infusion and 1 hour (± 15 minutes) post-infusion for the first 24 hrs of DPR
- Vital signs every 6 hrs (± 30 minutes): HR, RR, MAP/BP, SpO₂
- Weight
- Strict intake/output every 6 hrs (± 30 minutes)
- DPR Group research labs every 6 hrs (± 30 minutes):
 - Sodium
 - Potassium
 - Glucose
 - Lactate
- Adverse events

Day of Life 1 - Day of Life 7

- Instill DPR for DPR group every 6 hrs (± 30 minutes) until abdomen is closed
- Blood glucose within 1 hour prior to infusion and 1 hour (± 15 minutes) post-infusion for the first 24 hrs of DPR
- Vital signs every 6 hrs (± 30 minutes) for 48 hours after maximum dialysate infusion volume (100 mL) is reached, then every 12 hrs (± 30 minutes): HR, RR, MAP/BP, SpO₂
- Weight
- Strict intake/output every 6 hrs (± 30 minutes) for 48 hours after maximum dialysate infusion volume (100 mL) is reached, then every 12 hrs (± 30 minutes)
- Routine daily labs per NICU standard practice:
 - Complete CBC
 - Magnesium
 - Renal Function Panel (sodium, potassium, chloride, CO₂, BUN, creatinine, calcium, phosphate, albumin, glucose)

Title: Direct Peritoneal Resuscitation in Gastroschisis

PI: [name]

Sponsor: UAMS

- SoC Group research lab (every 24 hrs (\pm 30 minutes) at the same time as routine daily labs:
 - Lactate
- DPR Group research labs every 6 hrs (\pm 30 minutes) for 24 hours after maximum dialysate infusion volume (100 mL) is reached, then every 12 hrs (\pm 30 minutes):
 - Sodium
 - Potassium

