Other possible adverse reactions may include lactic-acidosis, fungal peritonitis, peritonitis bacterial, catheter-related infections, hypovolemia, hypervolemia, fluid retention, hypokalemia, hyponatremia, dehydration, hypochloremia, hypotension, hypertension, dyspnea, peritonitis, peritoneal cloudy effluent, vomiting, diarrhea, nausea, constipation, abdominal pain, abdominal distension, abdominal discomfort, Stevens-Johnson syndrome, urticaria, rash (including pruritic, erythematous and generalized), pruritus, myalgia, muscle spasms, musculoskeletal pain, generalized edema, pyrexia, malaise, infusion site pain, and catheter related complication.

Potential benefits for these subjects include earlier closure, fewer ventilator days, earlier feeding and decreased length of stay.

There will be no direct benefits to the study participants in the SoC group; however, knowledge gained from the study could potentially benefit subjects in the future as it guides us in best practices for pediatric patients with gastroschisis.

Subject Withdrawal from Study

Subjects' parent(s)/LAR may choose to withdraw from the study for any reason. Additionally, the investigator may choose to remove subjects from the study. This may occur for the following reasons:

- Serious adverse event believed to be related to investigational product
- Intolerable side effects
- Clinically significant laboratory abnormalities
- The investigator believes it is in the best interest of the subject to discontinue the study

Any subject withdrawing their consent to participate in the study or their authorization to use their protected health information will be withdrawn from the study. Neonates who are withdrawn from the study will no longer undergo any study-related procedures or data collection. Standard of care treatment will be continued.

Reasons why subjects are discontinued from the clinical trial will be documented on the Study Termination Form.

Safety Monitoring

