Given the risk for fluid and electrolyte imbalances, close monitoring will be provided for the DPR group by using more frequent clinical and laboratory assessments in addition to standard NICU monitoring. Vital signs and strict intake and output will be monitored every 6 hrs for 48 hours after maximum dialysate infusion volume (100 mL) is reached, then every 12 hrs (\pm 30 minutes). Sodium, potassium, blood glucose and lactate levels will be monitored every 6 hours (\pm 30 minutes) via heelstick, central/arterial line or venipuncture per NICU standard practice for 24 hours after the maximum dialysate infusion volume is reached, then every 12 hrs (\pm 30 minutes) through Post-Closure Day 1.

Title: Direct Peritoneal Resuscitation in Gastroschisis

PI: [name]

Sponsor: UAMS

Subject will also be monitored for the following potential adverse events:

1. Hypokalemia: If the potassium falls to <3.0, additional potassium will be added to the IV fluid at the discretion of the treating and study physicians.
2. Lactic acidosis: Lactate levels will be monitored with laboratory checks at least every 12 hours during the treatment phase. Continued monitoring of lactic acidosis will include laboratory checks, fluid replacement, and stopping infusion of the dialysate fluid.
3. Hyperglycemia: During the first day (24 hrs) of treatment, blood glucose will be obtained within 1 hour prior to infusion and 1 hour (\pm 15 minutes) post-infusion in addition to routine daily assessments. The neonatologists will change IVFs to contain less dextrose as needed.
4. Hypovolemia: This will be treated with fluid replacement. Blood pressure monitoring and urine output assessment will guide management for amount of fluid replacement needed.
5. Peritonitis: This will be evaluated daily by examination of the effluent dialysate for any cloudiness. Cloudy fluid will be sent to the laboratory for cell count, gram stain, and culture. If the cell count is elevated, the subject will receive antibiotics as indicated. Subjects with confirmed peritonitis will be withdrawn from the study.
6. Definite (culture positive) sepsis: Neonates with active clinical sepsis will be excluded from the study by the hemodynamic parameter exclusion criteria (hypotension, hyper/hypoglycemia, lactic acidosis, etc.). During the dialysate infusion period, subjects who develop definite (culture positive) sepsis will be withdrawn from the study.

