7. Acute Kidney Injury (AKI): AKI will be staged using the “Neonatal AKI KDIGO Classification” Table below (Selewski *et al* [22]). Subjects who develop AKI > Stage 2 will be withdrawn from the study.

TABLE 1 Neonatal AKI KDIGO Classification

Stage	SCr	Urine Output
0	No change in SCr or rise <0.3 mg/dL	≥ 0.5 mL/kg/h
1	SCr rise ≥ 0.3 mg/dL within 48 h or SCr rise $\geq 1.5\text{--}1.9 \times$ reference SCr ^a within 7 d	<0.5 mL/kg/h for 6 to 12 h
2	SCr rise $\geq 2.0\text{--}2.9 \times$ reference SCr ^a	<0.5 mL/kg/h for ≥ 12 h
3	SCr rise $\geq 3 \times$ reference SCr ^a or SCr ≥ 2.5 mg/dL ^b or Receipt of dialysis	<0.3 mL/kg/h for ≥ 24 h or anuria for ≥ 12 h

Differences between the proposed neonatal AKI definition and KDIGO include the following:

^a Reference SCr will be defined as the lowest previous SCr value.

^b SCr value of 2.5 mg/dL represents <10 mL/min/1.73m².

Individual Subject Discontinuation

If a subject develops any of the individual subject discontinuation criteria below, the study drug will be immediately discontinued:

- Positive blood culture
- Documented peritonitis
- Lactic acid > 5 mmol/L
- pH < 7.1
- Sodium < 125 mEq/L or > 150 mEq/L
- Potassium < 2.5 mEq/L
- Continued hyperglycemia > 250 for more than 12 hours
- Definite (culture positive) sepsis
- Stage 3 AKI [22]

Title: Direct Peritoneal Resuscitation in Gastroschisis

PI: [name]

Sponsor: UAMS

Subjects who develop any of the individual subject discontinuation criteria will be evaluated and monitored until resolution of the adverse events and laboratory values have returned to baseline. These subjects will no longer receive DPR, but will continue with assessments per the schedule of procedures and assessments.

Study Discontinuation

The study will be stopped if more than 3 subjects in the DPR group develop any one of the individual subject discontinuation criterion above.

Adverse Events

For purposes of this study, the following will be considered adverse events of special interest if they occur before study completion:

1. Bradycardia: defined as a heart rate < 100 bpm for ≥ 20 seconds
2. Desaturation: defined as SpO₂ < 80% for ≥ 20 seconds
3. A sustained apnea event defined as lasting ≥ 20 seconds and coinciding with at least one of the following:
 - HR < 100 bpm
 - Desaturation (oxygen saturation < 80%)
4. Other AES of special interest have been adopted from England *et al.*'s adverse event tables for the Pediatric Trials Network (PTN) [23] (Appendix E).

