All AEs will be recorded by the Investigator from the time of the start of study drug through the end of the designated follow-up period. All AEs will be recorded on the AE CRF. All relevant historical medical conditions that are known/diagnosed prior to the administration of study drug(s) are to be recorded.

Abnormal Laboratory Values Defined as AEs

An abnormal laboratory value is considered to be an AE if the laboratory abnormality is characterized by any of the following:

- Results in discontinuation from the study
- Requires treatment, modification of study drug dose, or any other therapeutic intervention
- Is judged by the Investigator to be of significant clinical impact/importance
- Grade 3 or Grade 4 lab abnormalities regardless of significance

If a laboratory abnormality is one component of a diagnosis or syndrome, then only the diagnosis or syndrome should be recorded as an AE. If the laboratory abnormality was not a part of a diagnosis or syndrome, then the abnormality should be recorded as the AE.

Monitoring, Recording and Reporting of AEs

All AEs occurring during the study period must be recorded. The clinical course of each event should be followed until resolution, stabilization, or until it has been determined that the study treatment or participation is not the cause. SAEs that are still ongoing at the end of the study period must be followed for up to 30 days to determine the final outcome. Any SAE that occurs after the study period and is considered to be possibly related to the study treatment or study participation should be recorded and reported immediately to the Sponsor.

All subjects will be monitored for AEs during the study. Assessments may include monitoring the subject's clinical symptoms; laboratory, pathological, radiological, or surgical findings; physical examination; or other appropriate tests and procedures.

Title: Direct Peritoneal Resuscitation in Gastroschisis

PI: [name]

Sponsor: UAMS

AE data collection and reporting, which are required as part of every study, are done to ensure the safety of subjects enrolled in the studies and those who will enroll in future protocols. AEs are to be reported in a routine fashion at scheduled times during the trial, such as with the annual continuing review to the IRB. Certain AEs must be reported in an expedited fashion to allow for timely monitoring of subject safety and care.

The reporting of these events depends on the characteristics of the event:

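### The protocol both ends and continues data collection for infants with peritonitis, culture-positive sepsis or AKI above Stage 2, and the likely loss falls mainly on the DPR arm

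*Combined protocol and SAP*

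**What the plan says.** Four parts of the protocol bear on what happens to an infant with one of these events.

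- **Safety Monitoring, items 5 to 7**, removes the infant. Peritonitis: "Subjects with confirmed peritonitis will be withdrawn from the study". Sepsis: "During the dialysate infusion period, subjects who develop definite (culture positive) sepsis will be withdrawn from the study". Kidney injury: "Subjects who develop AKI > Stage 2 will be withdrawn from the study".
- **Subject Withdrawal from Study** defines the consequence: "Neonates who are withdrawn from the study will no longer undergo any study-related procedures or data collection".
- **Individual Subject Discontinuation** lists documented peritonitis, definite sepsis and Stage 3 AKI among the reasons to stop study drug, and then says: "These subjects will no longer receive DPR, but will continue with assessments per the schedule of procedures and assessments".
- **Monitoring, Recording and Reporting of AEs** adds: "The clinical course of each event should be followed until resolution, stabilization", or until study treatment or participation is ruled out as the cause. Footnote 11 of the Calendar of Procedures and Assessments says much the same: "The clinical course of each AE should be followed until resolution, stabilization".

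Data Analysis gives the primary outcome, the tests and the sample size. It names no analysis population and has no rule for an infant whose time to full feeds was not collected. The only replacement rule, in the note under Eligibility Criteria, covers infants found to be ineligible.

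**The concern.** Staff cannot both end data collection and continue scheduled assessments for the same infant, and the analysis section does not settle which rule applies.

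The events occur after randomisation, and the arms are not equally exposed to the rules. SoC infants receive no dialysate, so a sepsis rule tied to the dialysate infusion period falls on DPR. Peritonitis is looked for in the effluent dialysate, so that rule probably falls mainly on DPR, although it names no arm and Risks and Benefits lists peritoneal inflammation as a risk in both groups. The AKI rule names no arm, and no direction is claimed for it.

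Under the withdrawal wording, time to full feeds, days on TPN, length of stay and the later course of adverse events would be missing for the infants most relevant to the second primary objective, which is to show no significant changes in safety parameters. The triggering event itself would still be recorded and would count towards study stopping.

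**Working it through.** **1. Do the rules cover the same infants?** Yes. Peritonitis and culture-positive sepsis appear in both lists. In the protocol's Table 1 the AKI stages run from 0 to 3, so AKI above Stage 2 and Stage 3 AKI are the same set. The contradiction needs no assumption.

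**2. Inputs for the size of the effect.** From Data Analysis: 20 infants per arm, SD 7 days, two-sided 5% test, target difference 6 days. (The stated power of at least 80% does not reproduce from these inputs: an exact t-test gives 75.2%. That is a separate matter and is not used here.) The documents give neither the rate of these events nor a feeding delay, so both are assumptions: event rate p, equal in the two arms, and delay L of 7 or 14 days. The 12.5% in Risks and Benefits is infection after standard repair, not a rate for these events; it serves only as one scenario. All removals are taken to fall in DPR.

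**3. Shift in the mean.** With no true effect, each arm's full mean is μ + pL. If DPR infants with the event are dropped and SoC infants kept, the observed DPR mean is μ, so the difference DPR − SoC is −pL:

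- p = 5%: 0.05 × 7 = 0.35 and 0.05 × 14 = 0.70 days
- p = 12.5%: 0.125 × 7 = 0.875 and 0.125 × 14 = 1.75 days

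For scale, the standard error of the difference is 7 × √(2/20) = 2.2 days.

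**4. Chance of losing at least one DPR infant**, 1 − (1 − p)^20: 64% at 5% (expected loss 1.0 of 20) and 93% at 12.5% (expected loss 2.5).

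**5. False-benefit rate.** Simulation with 200,000 trials per setting, normal data, SD 7 within the event and non-event groups, pooled two-sided t-test; false benefit means significant in favour of DPR, nominally 2.5%.

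| Assumed rate | Shift towards DPR, delay 7 / 14 days | False benefit, delay 7 / 14 days |
|---|---|---|
| 2.5% | 0.18 / 0.35 days | 3.0% / 3.4% |
| 5% | 0.35 / 0.70 days | 3.5% / 4.5% |
| 12.5% | 0.88 / 1.75 days | 5.4% / 8.8% |
| 20% | 1.40 / 2.80 days | 7.7% / 15.0% |

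If the infants are dropped from both arms, or all are kept, the shift is about 0 and false benefit about 2.5%.

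**6. Effect of the stopping rule.** The rule reads: "The study will be stopped if more than 3 subjects in the DPR group develop any one of the individual subject discontinuation criterion above". It can be counted across all criteria or separately for each.

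- Across criteria, the chance of stopping is P(Bin(20, p) > 3) = 1.6% at 5%, 23.5% at 12.5% and 58.9% at 20%. If a stopped trial yields no efficacy test, false benefit as a share of all trials started is 3.4% to 4.4% at 5% and 4.2% to 7.0% at 12.5%. With every infant kept under the same rule it is 2.3% to 2.4% at 12.5%.
- Per criterion, with events split equally over two criteria (an assumption), about 6.5% of trials stop at 12.5%, and false benefit is 5.1% to 8.3% of trials started.

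The other discontinuation criteria would add to stopping and are not modelled.

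**The case against.** The strongest reply is that there may be no real conflict. Individual Subject Discontinuation is the specific rule: it names these events and continues assessments. The sentence that ends data collection directly follows one on withdrawal of consent or authorisation and may have been meant only for that case. This reading is possible, but the sentence is not limited to consent, and the same section also provides for removal by the investigator. Even on the narrow reading, the protocol still calls these infants withdrawn in one place and under continued assessment in another.

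A second reply is that the bias needs a chain of conditions: the withdrawal wording prevails, removals fall mainly on DPR, the affected infants feed later, and the analysis uses complete cases. That is correct, so the bias is stated only as conditional.

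Third, the rates may be too high. Infusion generally lasts 3 to 5 days and at most 7, all infants receive 5 days of antibiotics, and 12.5% covers any infection after repair. Risks and Benefits calls the drain-related infection risk unknown but estimates it as not appreciably or substantially higher than 12.5%. This is a fair reason to give the lower rows more weight. None of these figures is a rate for the three events, so 12.5% is neither a best estimate nor an upper bound.

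Fourth, the simulation puts SD 7 inside each subgroup, so at 12.5% and 14 days the SoC SD is √(49 + 0.125 × 0.875 × 14²) = 8.4 rather than 7. Holding the total SD at 7 raises the 8.8% to about 11%, so this choice does not exaggerate the problem.

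**Conclusion.** The concern holds. The contradiction over data collection is certain from the text, and Data Analysis does not resolve it. The direction of any bias is conditional: towards DPR if the withdrawal wording is applied, the removals fall mainly on DPR, and the affected infants feed later.

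At the lower assumed rates the shift is small beside the 6-day target: at 5%, 6% to 12% of it (0.35/6 to 0.70/6). At 12.5% it is 15% to 29% (0.88/6 to 1.75/6), and the one-sided error is roughly two to three and a half times nominal before any stopping. If only some removals are specific to DPR, the shift falls roughly in proportion; if assessments continue, or removal is equal in both arms, it vanishes. The point should be fixed because primary-outcome data would be lost in a way related to treatment, and the loss is avoidable: the Data to be obtained section lists reaching 100 kcal/kg/day among items already in the medical record.

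**What to change.** 1. Reconcile Subject Withdrawal from Study, Safety Monitoring items 5 to 7, Individual Subject Discontinuation and the adverse-event follow-up rule, so that stopping DPR or study procedures is distinct from ending data collection. State that for these infants the primary and secondary outcomes, adverse events and 90-day follow-up are still abstracted from the medical record. Which study procedures, ultrasounds or research blood draws continue is for the sponsor to reconcile; none is proposed here.
2. Limit the end of data collection to withdrawal of consent or of authorisation to use health information.
3. State in Data Analysis that all randomised infants whose data may be used are analysed in their assigned arm. The only exception should be infants found ineligible on pre-treatment samples, judged by the same rule in both arms. This matters because the eligibility note ties the laboratory check to DPR administration, which SoC infants do not have.

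The cost is protocol wording plus minor extra chart abstraction for the few infants concerned. The change requires no extra blood draws or procedures.

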- Liver function test abnormalities defined as AST > 200 , ALT > 200 , GGT > 100 [19]
- Electrolyte abnormalities, defined as:
 - Sodium < 130 or $> 150 \text{ mEq/L}$
 - Potassium < 3.0 or $> 6.5 \text{ mEq/L}$
- Hyperglycemia ($> 150 \text{ mg/dL}$) or hypoglycemia ($< 40 \text{ mg/dL}$)

Note: Potentially eligible subjects may be randomized and the silo placed according to the assigned study arm before all laboratory results are available. Laboratory values will be verified for eligibility prior to administration of DPR. Any ineligible subjects will be withdrawn from the study and may be replaced.

Randomization

The randomization schedule will be generated by the biostatistics department and the Principal Investigator (PI) will maintain a randomization log listing the subjects' ID and study arm assignment. Subjects will be randomized to either the DPR group or SoC group. If the subject is assigned to receive DPR, the ACRI Research Pharmacist will dispense the 1.5% Dianeal solution. The PI will calculate the dose to be distributed based on the subject's weight at the time of enrollment and administer the appropriate volume of 1.5% Dianeal solution as per instructions in the *Investigational Product* section.

Study Design and Procedures

This is a prospective double-arm study designed to evaluate the tolerability of direct peritoneal resuscitation (DPR) in neonates with gastroschisis. The experimental arm (DPR group) will receive adjuvant DPR with standard treatment for gastroschisis (staged silo closure). The control arm (SoC group) will receive standard treatment for gastroschisis only. All subjects will be placed in a silo shortly after birth and within 2 hours of admission to the NICU and subsequently serially reduced in silo with umbilical tape until the bowel contents are at the level of fascia and deemed suitable for closure.

A. SoC Group

[figure not shown]
The SoC group will be placed in silo within 2 hours of admission to the NICU per standard practice. These subjects will have no change in current clinical management by the neonatologists or pediatric surgeons and will not receive peritoneal dialysis fluid.

B. DPR Group

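### Adverse-event recording starts at first study drug, which gives the SoC arm no start and places DPR drain insertion before the record opens

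*Combined protocol and SAP*

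**What the plan says.** The only explicit start for adverse-event (AE) recording is in the protocol's Study Period section: "All AEs will be recorded by the Investigator from the time of the start of study drug". The same paragraph adds: "All relevant historical medical conditions that are known/diagnosed prior to the administration of study drug(s) are to be recorded".

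Three other parts of the protocol bear on that start.

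- **Arms.** Under SoC Group, these infants "will not receive peritoneal dialysis fluid". Under DPR Group and Set-up of Silo, the drain goes in beneath the fascia when the silo is placed, within 2 hours of NICU admission.
- **Order of events.** The note after the exclusion criteria says "Potentially eligible subjects may be randomized and the silo placed according to the assigned study arm before all laboratory results are available". It continues: "Laboratory values will be verified for eligibility prior to administration of DPR". Then: "Any ineligible subjects will be withdrawn from the study and may be replaced". Subject Withdrawal from Study ends study procedures and data collection for withdrawn neonates.
- **Schedule.** In the Schedule of Procedures and Assessments, the Screening block includes "JP drain placed and secured per randomization" but no AE item. The next block, whose heading begins "Staged Reduction Day 1 (Day of Birth from 0-24 hours", lists adverse events with no arm label.

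**The concern.** A recording window should open at a point that every randomized infant reaches, and no later than the first procedure that differs between arms. The start of study drug meets neither condition. One arm never reaches it, and in the other arm it comes after the drain, which is itself part of the experimental treatment.

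This matters because Risks and Benefits says that the infection risk of placing and keeping the drain is unknown, and because safety is primary objective 2. If the Study Period sentence is followed as written, the arms do not share an AE window and their rates cannot be compared on the same basis. A complication of inserting the drain could also be entered as a pre-existing condition.

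**Working it through.** No figure in the plan depends on the AE start, so there is no stated result to reproduce. The check sets the sections side by side and sizes what can be sized.

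**1. SoC arm.** The start is first study drug (Study Period), and SoC infants receive none (SoC Group). The sentence therefore sets no start for 20 of 40 planned infants (Study Population; Data Analysis): 20/40 = 50%.

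**2. DPR arm.** The sequence is randomization, then silo and drain, then laboratory verification, then first infusion. Dialysate is given through the drain, so insertion always precedes the AE start.

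**3. Length of the DPR gap.**
- Upper bound: the schedule lists laboratory verification and first instillation in the 0-24 hour block, so drain-to-infusion is above 0 and under 24 h. Against closure at 3-5 days (Investigational Product), 24/72 = 33% and 24/120 = 20%.
- One case with a lower bound: the lactate criterion needs two values above 5 mmol/L at least 6 h apart. If the first is high, was drawn at or after NICU admission, and the repeat is awaited, the gap is at least 6 - 2 = 4 h.

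**4. Infections within the gap, for infants who stay.** Risks and Benefits quotes 12.5% for standard repair. Applied to 20 infants, 0.125 x 20 = 2.5. Spread evenly over 5 days (an assumption), an assumed 2 h gap holds 2.5 x 2/120 = 0.04 infants and a 24 h gap holds 2.5 x 24/120 = 0.5. The 12.5% is not tied to the first 5 days, so these are upper figures. Infection counts in retained infants are therefore little affected; the gap matters mainly for events at insertion.

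**5. Does other text supply a common start?**
- The AE definition refers to the course of the study and gives no starting event.
- The statement that all subjects are monitored during the study gives no starting event either.
- Events of special interest count if they occur before study completion, which fixes an end and not a beginning.
- The later reference to AEs in the study period leads back to the section of that name.
- The unlabelled AE item in the 0-24 hour block conflicts with the Study Period sentence for SoC. That block overlaps the 0-12 hour screening window, but the Screening list, where the drain is placed, has no AE item.
- The Calendar table appears to mark AE assessment under Screening. Its columns may have shifted in extraction from the PDF (instillation also appears there), so it cannot settle the point.

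**6. Drained, then ineligible.** These infants carry the insertion risk, never reach first drug, and leave further data collection on withdrawal. The documents give no rate of laboratory ineligibility, so their number cannot be derived.

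**The case against.** The best reply is that the protocol plainly intends AE collection in both arms: all subjects are monitored, the AE definition is not tied to drug, special-interest events include infections, and the day-of-birth AE item carries no arm label. This stands. A reader might infer from the Study Period sentence that SoC events are excluded; the documents do not support that. They show an undefined start and an internal conflict, not an exclusion.

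A reader might also infer that every insertion event would be lost. That goes too far. Drain infections and surgical complications are among the items listed under Data to be obtained, earlier conditions are recorded as history, and an unexpected, research-related event that involves new or increased risk goes to the IRB. Events can be misfiled without being lost. These routes are still partial. Risks and Benefits already lists catheter-related infections and complications, so such an event would normally count as expected in type unless its severity exceeds what is listed. The continuing-review route depends on the event having been recorded as an AE.

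On withdrawal, the protocol ends only further data collection. It does not discard what is already recorded, it follows each AE to resolution or stabilization, and it asks for possibly related SAEs after the study period to be reported. Infants who merely stop DPR under the individual discontinuation criteria stay on the assessment schedule. What remains uncovered is later non-serious drain events in infants drained and then withdrawn as ineligible. It would be tempting to say how far this understates the drain event rate, but the documents give neither the number of such infants nor their event rate, and do not say that they leave the safety denominator.

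**Conclusion.** The point holds as a conflict to be reconciled. The one explicit start rule has no meaning for half the planned infants and falls after drain insertion in the other half, and no other passage sets a common start. In the DPR arm the uncovered interval is under 24 hours, on the assumption that the schedule is followed. The expected number of infections inside it is small (0.04-0.5 infants under the assumptions above), so the consequence lies mainly in insertion events, the missing SoC start, and an unknown number of drained-then-withdrawn infants. No planned analysis is shown to give a wrong result. It should be corrected because drain risk is described as unknown and safety is a primary objective.

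**What to change.** - **Study Period:** start AE recording at randomization, before silo or drain placement, in both arms. Use the same point to separate medical history from AEs in the sentence that follows.
- **Schedule and Calendar:** list adverse events under Screening in the Schedule of Procedures and Assessments, and make the Calendar agree.
- **Subject Withdrawal from Study:** state that an infant who had a drain placed and is then withdrawn as lab-ineligible stays in AE follow-up unless the parent withdraws permission for data use.

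The cost is wording in these sections and in the consent form, an AE window longer by less than a day, and AE follow-up of any drained-then-ineligible infants. No new tests are needed, and no dose or clinical rule changes.
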